3.8.2.3. Examination of Subgroups

Subgroup analyses of the primary endpoint will be performed for each of the following subgroup.

- Sex (male, female)
- Age (<55 years, ≥55 years)
- Race (white, black or African American, other)
- Region (US, non-US)
- Baseline PANSS total score (<95 points, ≥95 points)

The forest plot of the least squares mean difference along with 95% CI between ALKS 3831 and placebo will be provided by the subgroup factors listed above.

3.8.3. Key Secondary Endpoint

The key secondary efficacy endpoint is change from baseline in CGI-S at Week 4.

Primary Analysis

An MMRM analysis, similar to the primary analysis on primary endpoint ([Section 3.8.2.1](#)) will be conducted to analyze the difference between ALKS 3831 and placebo groups.

Sensitivity Analysis

To assess the impact of missing data, a Delta-adjusted Pattern Mixture Model³ similar to the sensitivity analysis of the primary endpoint in [Section 3.8.2.2](#) will be conducted.

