### 14.4.2. Key Secondary Endpoint

The key secondary endpoint is change from baseline in CGI-S score at Week 4.

The analysis will be carried out using MMRM as described for the primary endpoint.

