3.8.2.1. Primary Analysis

For the primary efficacy endpoint, change from baseline in PANSS total score at Week 4, primary analysis will be carried out using a mixed model with repeated measurements (MMRM) with an unstructured variance-covariance matrix based on the observed data for the FAS population. The model will include region (US vs. non-US), visit, treatment, and interaction term of visit and treatment as categorical variables, and baseline PANSS total score as a covariate. The Kenward-Roger approximation² will be used to adjust the denominator degree of freedom. The change from baseline in PANSS total score at Week 4 in the ALKS 3831 group will be compared to that in the placebo group using superiority testing at two-sided alpha level of 0.05. The least squares (LS) mean, standard error (SE), and LS mean difference between ALKS 3831 and placebo along with the 95% CI, will be summarized.

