3.8.4. Multiple Comparison / Multiplicity

If the primary analysis of the primary endpoint is statistically significant between ALKS 3831 and placebo, the statistical test will be performed on the key secondary efficacy endpoint between ALKS 3831 and placebo at two-sided alpha of 0.05.

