3.8.5. Other Endpoints

- Change from baseline in PANSS total score and PANSS subscales (positive, negative, general psychopathology) by visit
- Change from baseline in CGI-S by visit
- CGI-I at each post-Baseline visit
- PANSS responders ($\geq 30\%$ improvement from baseline in PANSS total score) by visit
- CGI-I responders (CGI-I score of 2 [much improved] or 1 [very much improved]) by visit
- Overall Response defined as: PANSS total score $\geq 30\%$ improvement from baseline or CGI-I score of 1 or 2 by visit
- Change from baseline in PANSS-Excited Component (EC) score (comprised of 5 items, excitement, tension, hostility, uncooperativeness, and poor impulse control) by visit
- Change from baseline in MOAS score by visit

The CGI-I score at each postbaseline visit will be summarized by descriptive statistics.

For proportion of subjects exhibiting improvement on the CGI-I assessment (CGI-I score of ≤ 2), a logistic regression based on LOCF imputation for missing data will be used to compare ALKS 3831 with placebo. The model will include the region (US vs. non-US) and treatment group as factors, and baseline PANSS total score as covariates.

All other endpoints will be summarized by treatment group for all visits. Each active group (ALKS 3831 or olanzapine) will be compared to placebo. For continuous outcome, a similar approach to that for the primary endpoint will be used ([Section 3.8.2.1](#)). For dichotomous outcomes, a similar approach to that used for CGI-I improvement scores will be used, using LOCF to impute for missing data and adjusting for their corresponding baseline values.

For subjects with MOAS total score of at least 1 at baseline, the change from baseline in MOAS score and subscales will be analyzed using a similar MMRM model as [Section 3.8.2.1](#), adjusting for baseline value as covariate.

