5. CHANGES IN CONDUCT OR PLANNED ANALYSES FROM THE PROTOCOL

Changes have being made to the analyses specified in the [Protocol](#)¹ Section 14.4 to include the region (US vs. non-US) as a factor in the analysis model for all the relevant efficacy endpoints as described above.

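### Read literally, the key secondary CGI-S model adjusts only for baseline PANSS total and never names baseline CGI-S; the test stays valid, but some precision is given up

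*SAP*

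**What the plan says.** - **Key secondary model.** Protocol 14.4.2: "The analysis will be carried out using MMRM as described for the primary endpoint". SAP 3.8.3 uses a looser word: "An MMRM analysis, similar to the primary analysis on primary endpoint", with a pointer to 3.8.2.1. Neither section lists the covariates.
- **The model pointed to.** SAP 3.8.2.1 has region, visit, treatment and visit-by-treatment "as categorical variables, and baseline PANSS total score as a covariate". Protocol 14.4.1 has the same single baseline covariate, without region.
- **CGI-S sensitivity analysis.** SAP 3.8.3 calls for a delta-adjusted analysis on the pattern of 3.8.2.2, where the ANCOVA covariate is baseline PANSS.
- **Where an own baseline is named.** SAP 3.8.5 also builds the MOAS model on 3.8.2.1, but adds "adjusting for baseline value as covariate". For dichotomous outcomes it adds "adjusting for their corresponding baseline values".
- **Where it is not named.** SAP 3.8.5 gives no baseline covariate for the PANSS subscales or PANSS-EC, which follow the primary approach by cross-reference.
- **Declared changes.** SAP section 5 records one change from the protocol models: "to include the region (US vs. non-US) as a factor in the analysis model for all the relevant efficacy endpoints". It mentions no change of baseline covariate.
- **Role of the test.** If the primary analysis is significant, SAP 3.8.4 tests the "key secondary efficacy endpoint between ALKS 3831 and placebo at two-sided alpha of 0.05".

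**The concern.** A model for change from baseline normally carries the baseline of the same measure. In the PANSS model it does, because baseline PANSS total is that baseline. When the model is carried over to CGI-S by reference, the literal result is change in CGI-S adjusted for a different scale.

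Two things are at stake. The first is precision: baseline PANSS total is only a partial stand-in for baseline CGI-S, so some explainable variation stays in the error term, and a chance difference between arms in baseline CGI-S is only partly adjusted. The second is pre-specification. One programmer could keep PANSS total, another could substitute CGI-S, and each could defend the choice from the text. The two models would give different estimates and p-values for the only secondary endpoint in the testing sequence.

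**Working it through.** **The plan's own figure.** The only power statement (Protocol 14.1, SAP 2) concerns PANSS: 130 per arm, 30% dropout, difference 10, SD 20, two-sided 0.05. Evaluable per arm: 130 × 0.7 = 91. Standard error: 20 × √(2/91) = 2.965. Power: Φ(10/2.965 − 1.960) = Φ(1.413) = 92.1%, which agrees with the stated minimum of 90%. It does not depend on the CGI-S covariate. The documents give no SD, effect or correlation for CGI-S, so everything below rests on assumptions.

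**Notation.** B = baseline CGI-S (SD s_B), Y = Week 4 CGI-S (SD s_Y), P = baseline PANSS total scaled to SD 1. Correlations: ρ = corr(Y,B), r = corr(B,P), q = corr(Y,P).

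**Formulas** (Week 4 ANCOVA with complete data, as an approximation to the MMRM):
- PANSS only: V_P = s_Y² + s_B² − 2ρ·s_Y·s_B − (q·s_Y − r·s_B)²
- Both covariates: V_BP = s_Y²·[1 − (ρ² + q² − 2ρqr)/(1 − r²)]
- Difference: V_P − V_BP = (b − 1)²·s_B²·(1 − r²), where b = [(ρ − qr)/(1 − r²)]·(s_Y/s_B) is the slope of Y on B given P.

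The difference is a square, so the PANSS-only residual variance can never be the smaller of the two.

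**Worked example.** Take s_B = 0.6, s_Y = 1.1, ρ = 0.3, r = 0.5, q = ρr = 0.15.
- V_P = 1.21 + 0.36 − 0.396 − (0.165 − 0.300)² = 1.174 − 0.018 = 1.156
- V_BP = 1.21 × (1 − 0.09) = 1.101 (with q = ρr the bracket reduces to 1 − ρ²)
- Ratio = 1.05. Check: b = 0.55, and 0.45² × 0.36 × 0.75 = 0.055 = 1.156 − 1.101.

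**Grid.** s_B 0.6 or 0.7; s_Y 1.0, 1.1 or 1.2; ρ 0.2, 0.3, 0.4 or 0.5; r 0.5 or 0.6. That is 48 combinations for each choice of q.

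| q = corr(Week 4 CGI-S, baseline PANSS) | Median V_P/V_BP | Range |
|---|---|---|
| 0 | 1.02 | 1.00-1.15 |
| ρr (no link beyond baseline CGI-S) | 1.05 | 1.00-1.20 |
| 0.2 | 1.05 | 1.00-1.25 |
| 0.3 | 1.09 | 1.00-1.33 |

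The medians give the 2-9%. The 1.33 arises at s_B = 0.7, s_Y = 1.0, ρ = 0.2, r = 0.5, q = 0.3.

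**In power terms.** If the test with both covariates had 90% power (a reference point, not a figure in the plan), the PANSS-only test would have Φ(3.242/√ratio − 1.960), where 3.242 = 1.960 + 1.282. This gives 89.4% at 1.02, 88.6% at 1.05, 87.4% at 1.09 and 80.3% at 1.33.

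**A wider range.** With s_Y/s_B from 1 to 2, ρ 0.2-0.6, r 0.3-0.7 and q = ρr, the ratio runs from 1.00 to 1.61 (power about 72% to 90%). Ratios above about 1.2 occur there only at or near s_Y = s_B. Entry at CGI-S of 4 or more (Protocol 7.1) narrows the baseline spread, so equal SDs are not the likely case.

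**Substituting rather than adding.** PANSS-only against own-baseline-only has no fixed sign. On the 48-point grid the ratio is 1.00-1.20 when q = ρr, but 0.82-1.13 (median 0.95) when q = 0. Only adding baseline CGI-S while keeping PANSS total is sure not to increase the residual variance.

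**Imbalance.** If the arms have equal baseline PANSS but differ by Δ in baseline CGI-S, the PANSS-adjusted contrast moves by (b − 1)Δ. In the worked example, one standard error of Δ given PANSS is 0.6 × √(2/130) × √0.75 = 0.064, so the shift is 0.45 × 0.064 = 0.029 CGI-S points. This has mean zero over randomizations and is already part of the PANSS-only standard error.

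**The case against.** The strongest reply is that the SAP says similar, not identical. Baseline PANSS total is the primary outcome's own baseline, so the natural counterpart for CGI-S is baseline CGI-S. SAP 3.8.3 uses the same word for the delta-adjusted analysis, whose template imputes PANSS values and makes sense only if CGI-S replaces PANSS. The contrast with 3.8.5 is also imperfect. The dichotomous outcomes needed explicit wording because their template, the CGI-I responder model, names baseline PANSS, and the MOAS sentence describes a restricted subset. This stands to the extent that omission of baseline CGI-S is not proved. It does not remove the gap: the MOAS sentence cites the same section 3.8.2.1 and still names the baseline, the protocol says as described, and SAP section 5 declares no substitution.

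The documents also make some provision for imbalance. SAP 3.5 summarizes baseline CGI-S by arm, and Protocol 14.3 allows adjustment for important imbalances. That is fair, but such adjustment would be decided after seeing the data and is weaker than a covariate fixed in advance.

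A reader might infer more: that regression to the mean, sharpened by the CGI-S entry threshold, biases the treatment contrast, or that type I error is at risk. The documents do not support this. The threshold applies to all subjects before randomization, so regression to the mean is the same in expectation in each arm and cancels in the difference. Chance imbalance is random error that the standard error already reflects.

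**Conclusion.** The point holds as one of precision and pre-specification. Read literally, the CGI-S MMRM and its delta-adjusted ANCOVA carry baseline PANSS total as the only baseline covariate, and baseline CGI-S is named nowhere for this test. It would go too far to state as fact that CGI-S will be tested without its own baseline, because similar leaves room for the substitution.

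The comparison of ALKS 3831 with placebo is valid under either model, and no stated sample size, power or alpha changes. The likely cost of the literal model is small: residual variance typically about 2-9% larger than with both covariates, or about 0.6 to 2.6 power points from a 90% reference, and up to about 33% (about 10 points) at the edge of the main grid. These sizes rest on assumed SDs and correlations. In particular they depend on the correlation of Week 4 CGI-S with baseline PANSS, about which the documents say nothing.

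**What to change.** 1. In SAP 3.8.3, write the model out: *MMRM as in 3.8.2.1 with baseline CGI-S as a covariate, in addition to baseline PANSS total.*
2. Name the same covariates in the ANCOVA of the CGI-S delta-adjusted analysis.
3. In SAP 3.8.5, state that each continuous change-from-baseline endpoint adjusts for its own baseline. This covers the PANSS subscales and PANSS-EC.
4. List the change from Protocol 14.4.2 in SAP section 5, before unblinding.

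Baseline CGI-S is already collected at Visit 2 (Protocol Table 1), so no new data are needed. The cost is a few lines of SAP text and about one degree of freedom in the CGI-S model.

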3.8.4. Multiple Comparison / Multiplicity

If the primary analysis of the primary endpoint is statistically significant between ALKS 3831 and placebo, the statistical test will be performed on the key secondary efficacy endpoint between ALKS 3831 and placebo at two-sided alpha of 0.05.

3.8.5. Other Endpoints

- Change from baseline in PANSS total score and PANSS subscales (positive, negative, general psychopathology) by visit
- Change from baseline in CGI-S by visit
- CGI-I at each post-Baseline visit
- PANSS responders ($\geq 30\%$ improvement from baseline in PANSS total score) by visit
- CGI-I responders (CGI-I score of 2 [much improved] or 1 [very much improved]) by visit
- Overall Response defined as: PANSS total score $\geq 30\%$ improvement from baseline or CGI-I score of 1 or 2 by visit
- Change from baseline in PANSS-Excited Component (EC) score (comprised of 5 items, excitement, tension, hostility, uncooperativeness, and poor impulse control) by visit
- Change from baseline in MOAS score by visit

The CGI-I score at each postbaseline visit will be summarized by descriptive statistics.

For proportion of subjects exhibiting improvement on the CGI-I assessment (CGI-I score of ≤ 2), a logistic regression based on LOCF imputation for missing data will be used to compare ALKS 3831 with placebo. The model will include the region (US vs. non-US) and treatment group as factors, and baseline PANSS total score as covariates.

All other endpoints will be summarized by treatment group for all visits. Each active group (ALKS 3831 or olanzapine) will be compared to placebo. For continuous outcome, a similar approach to that for the primary endpoint will be used ([Section 3.8.2.1](#)). For dichotomous outcomes, a similar approach to that used for CGI-I improvement scores will be used, using LOCF to impute for missing data and adjusting for their corresponding baseline values.

For subjects with MOAS total score of at least 1 at baseline, the change from baseline in MOAS score and subscales will be analyzed using a similar MMRM model as [Section 3.8.2.1](#), adjusting for baseline value as covariate.

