### 14.4.3. Other Endpoints

- Change from baseline in PANSS total score and PANSS subscales (positive, negative, general psychopathology) by visit
- Change from baseline in MOAS score by visit
- Change from baseline in CGI-S by visit
- CGI-I at each postbaseline visit
- PANSS responders ( $\geq 30\%$  improvement from baseline in PANSS total score) by visit
- CGI-I responders (CGI-I score of 2 [much improved] or 1 [very much improved]) by visit
- Overall Response defined as: PANSS total score  $\geq 30\%$  improvement from baseline or CGI-I score of 1 or 2 by visit
- Change from baseline in PANSS-Excited Component (EC) score (comprised of 5 items, excitement, tension, hostility, uncooperativeness, and poor impulse control) by visit

For proportion of subjects exhibiting improvement on CGI-I assessment, a logistic regression based on last observation carried forward (LOCF) imputation for missing data will be used to

compare ALKS 3831 with placebo. The model will include treatment group, and baseline PANSS total score as covariates.

For all other endpoints, each point will be summarized by treatment groups for all visits. Each active group (ALKS 3831 or olanzapine) will be compared to placebo. For continuous outcome, a similar approach to that for PANSS total score will be used. For dichotomous outcome, a similar approach to that used for CGI-I improvement scores will be used. More details will be provided in the statistical analysis plan (SAP).

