2. SAMPLE SIZE CONSIDERATION

The planned sample size is 390 subjects in total, 130 subjects per treatment group. This sample size will provide at least 90% power to show superiority of the ALKS 3831 group compared to placebo group at a 2-sided alpha level of 0.05, assuming a 10-point improvement of PANSS total score at week 4, a standard deviation (SD) of 20, and a dropout rate of 30%.

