3.8.2.2. Sensitivity Analysis

To assess the robustness of the primary analysis of the primary endpoint, the following sensitivity analyses will be performed:

- Delta-adjusted Pattern Mixture Model³ will be conducted to assess the impact of missing data. It incorporates the clinical assumption that ALKS 3831 subjects who discontinue at a given time point would have, on average, their unobserved PANSS worsened by some amount δ compared with the observed PANSS of subjects on the same treatment arm who continue to the next timepoint. Subjects who discontinue from the placebo arm would have the same PANSS trajectory as the placebo subjects who stay on the study. A sequential regression-based multiple imputation (MI) procedure will be used to incorporate the assumption and to allow uncertainty in the imputations to be reflected appropriately in the analysis. The imputation model will

include the measurement at the current timepoint as the response variable, and region (US vs. non-US) as factor, the measurements at the previous timepoints and the baseline as covariates. Twenty imputations will be carried out. For each of the 20 imputed data sets, the ANCOVA model with region (US vs. non-US) and treatment group as factors and baseline PANSS as covariate will be fitted to the change from baseline at Week 4 to obtain the treatment effect estimate and standard error. Rubin's rule will be used to combine the treatment effect estimates and standard errors across imputations. The shift parameters to be used in the sensitivity analysis will account for 10%, 20%, 30%, 40%, and 50% of the observed treatment difference between ALKS 3831 and placebo.

- The MMRM model may adjust for additional covariates and/or factors.

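### LOCF is the only missing-data method for the three responder endpoints, and it can bias the comparison with placebo in either direction

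*SAP*

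**What the plan says.** For CGI-I response, SAP Section 3.8.5 states that "a logistic regression based on LOCF imputation for missing data will be used to compare ALKS 3831 with placebo". Other dichotomous endpoints, namely PANSS response (at least 30% improvement) and Overall Response, follow the same approach, "using LOCF to impute for missing data and adjusting for their corresponding baseline values". Protocol Section 14.4.3 carries the same rule: "For dichotomous outcome, a similar approach to that used for CGI-I improvement scores will be used".

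SAP Section 2 assumes "a dropout rate of 30" per cent. This is one overall figure, with no split by arm, time or reason.

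The primary endpoint uses the same PANSS ratings but is handled differently. It is analysed by MMRM on observed data (Section 3.8.2.1), with a delta-adjusted pattern mixture sensitivity analysis, for which "A sequential regression-based multiple imputation (MI) procedure will be used" (Section 3.8.2.2). The key secondary endpoint, CGI-S, is treated in the same way (Section 3.8.3). Neither document specifies a missing-data sensitivity analysis for a responder endpoint.

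**The concern.** LOCF assumes that a subject's response status would not have changed after the last rating, or that such changes cancel between arms. The trial enrols acutely ill subjects with a PANSS total of at least 80. It allows discharge from Week 2 at a total below 70 if the other criteria are met (Protocol Sections 7.1 and 8.1.1). It therefore expects scores to move during these four weeks. Protocol Section 7.3 lists both lack of efficacy and adverse events as reasons for withdrawal, and these could plausibly differ between drug and placebo.

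If one arm loses more subjects, or loses them earlier or for other reasons, its response rate is frozen at a different stage. The odds ratio then partly reflects who stayed. A PANSS result and its responder version could also disagree only because one assumes missing at random (MAR) and the other carries values forward. Response rates are easily read clinically and are likely to be quoted.

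**Working it through.** **1. The plan's own figure.** SAP Section 2 gives 130 per arm, a 10-point difference, SD 20, 30% dropout and two-sided alpha 0.05. Evaluable per arm: 130 × 0.70 = 91. Power = Φ(10 / (20 × √(2/91)) − 1.96) = Φ(3.37 − 1.96) = 92.1%. The stated power of at least 90% holds. It concerns the primary endpoint and says nothing about the responder analyses.

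**2. Formula for the LOCF bias.** Assume no true effect, dropout unrelated to outcome, and last ratings spread evenly over Weeks 1 to 3. Let p4 be the Week 4 response rate, p̄ the mean response rate over Weeks 1 to 3, and d the dropout proportion in an arm.

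- LOCF response rate in an arm = (1 − d) × p4 + d × p̄
- False difference, drug minus placebo = (d placebo − d drug) × (p4 − p̄)

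The response curves and dropout splits below are assumptions; n = 130 per arm comes from the SAP. The test is a two-sided 5% z-test.

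| Response, Weeks 1–4 | Dropout drug/placebo | False difference | Type I error |
|---|---|---|---|
| 10/22/32/40% | 30/30% | 0 | 5.0% |
| 10/22/32/40% | 25/35% | +1.9 points | 6.2% |
| 10/22/32/40% | 20/40% | +3.7 points | 9.7% |
| 10/22/32/40% | 40/20% | −3.7 points | 9.7% |
| 5/15/30/50% | 25/35% | +3.3 points | 8.5% |
| 5/15/30/50% | 20/40% | +6.7 points | 19.5% |
| 40% throughout | 20/40% | 0 | 5.0% |
| 45/44/42/40% | 20/40% | −0.7 points | 5.2% |

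Example, row 3: p̄ = (10 + 22 + 32)/3 = 21.3%, and 0.20 × (40 − 21.3) = 3.7 points.

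**3. Simulation on the PANSS scale, no true effect.** Assumed mean changes are −8/−13/−17/−20, with Week 4 SD 20, adjacent-visit correlation 0.85, baseline mean 95 or 100 and an unadjusted Wald test. Dropout is random within arm with a constant hazard h per interval, so total dropout = 1 − (1 − h)³. Hazards of 0.08 and 0.14 give 22% and 36%; 0.07 and 0.17 give 20% and 43%.

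- About 30/30%: difference about 0, type I error about 5%.
- Mild imbalance (hazards 0.10/0.12, about 27/32%): 0.6 to 1.0 points, 5.1% to 5.9%.
- 22/36%: about 1.8 points and 6.4% with SD 20 at every visit; 2.6 to 2.8 points and 8.1% to 8.6% with SDs 12/15/18/20.
- 20/43%: about 3 points and 8.2% to 8.4% with constant SD; 4.5 to 4.6 points and 13.5% with growing SD.
- 43/20%: −4.7 points, 13.8%, against the drug.

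A run that fixed only the Week 4 SD gave 3.2 points (9.8%) at 22/36% and 4.8 points (15.2%) at 20/43%. I read these as the upper end. In the unequal scenarios, within-arm multiple imputation followed by classification stayed within simulation error of 0, with type I error about 2% to 3%.

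**4. Dropout related to outcome.** Assumed mean changes are −8/−13/−16/−18, with SD 20 and correlation 0.75; only subjects worse than the visit mean can drop out for lack of efficacy.

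- Lack-of-efficacy dropout in both arms, 19/37%: +2.3 points, 7.2%.
- Nearly equal dropout (30/32%), random on drug but for lack of efficacy on placebo: +1.5 points (5.7%), or +4.0 points (11.2%) if the mean change is flat at −18.

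So unequal rates are not necessary for bias. When dropout depends on outcome, a flat mean does not remove it either, because individual ratings still move.

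**The case against.** The strongest reply is about consequence. The responder endpoints are listed as other endpoints. The testing sequence in SAP Section 3.8.4 contains only the primary and key secondary endpoints, and neither uses LOCF. Type I error carries little decision weight for tests without alpha control. PANSS and CGI-S by visit are also analysed by an MMRM-type model in the same section. All of this stands, and it limits the importance of the point.

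The sizes also depend on assumed trajectories, SDs and dropout splits, and the simulated test was not the SAP's covariate-adjusted logistic model. That stands too. In addition, withdrawn subjects are asked back for an early termination visit close to the last dose, with the Visit 6 assessments (Protocol Section 7.3 and Table 1). Where that rating is obtained and carried forward, it is later than the last weekly one, and the bias under a rising response would shrink. The simulations leave this out.

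Finally, multiple imputation without a shift assumes MAR, which is doubtful for lack-of-efficacy withdrawals, and non-responder imputation is an equally standard choice. This argues for an additional sensitivity analysis. It does not argue for LOCF alone.

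A reader might infer that LOCF produces a false difference whenever dropout differs by arm, or that it must favour the drug and make p-values too small. The documents do not support this. They give neither a dropout split nor a response curve. Under the formula above the bias is zero with a flat response, and it reverses if the drug arm loses more subjects.

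**Conclusion.** The point holds as a conditional one. LOCF is the sole specified method for three endpoints with 30% planned dropout. It conflicts with the assumption behind the MMRM on the same PANSS data, and it can distort the responder comparisons in either direction.

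With no true effect and dropout unrelated to outcome, the false difference is 0 under equal dropout or flat response. It is roughly 2 to 3 points at about 22/36% dropout, and 3 to 5 points at about 20/43% (type I error about 8% to 15%). With the steep response curve it reaches about 7 points at 20/40% (type I error 19.5%). Every split and trajectory is an assumption. A reader might also infer that the trial's main efficacy conclusion is at risk; it is not, since the primary and key secondary analyses do not use LOCF. The change is worth making because the better method is largely written into the SAP already.

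**What to change.** Amend SAP Section 3.8.5 before unblinding:

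- **PANSS response:** impute PANSS separately within each arm by the sequential-regression procedure of Section 3.8.2.2, with no shift. Classify response in each of the 20 data sets, fit the planned logistic model and pool by Rubin's rule.
- **CGI-I response:** use a separate imputation model suited to a seven-category rating without a baseline value, for example an ordinal one. The PANSS procedure does not transfer unchanged.
- **Overall Response:** derive it from the imputed PANSS and CGI-I values together.
- **Sensitivity:** add a delta-shifted imputation or non-responder imputation, because zero-shift imputation assumes MAR.
- **LOCF:** keep it as supportive.

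Apply the same rules to the olanzapine comparison with placebo. The cost is SAP wording and modest programming; no new data are needed.
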